STAT3	Signal Transducer and Activator of Transcription 3
TK	Tyrosine kinase
TSC2	Tuberous Sclerosis Complex 2
TUNNEL	Terminal deoxynucleotidyl transferase (TdT)-mediated dUTP-biotin Nick End Labeling
ULN	Upper limit of normal
VEGF	Vascular Endothelial Growth Factor
WBC	total white blood cell count

[figure not shown]
WHO World Health Organization

SCHEMA

[figure not shown]
Diagnosis of CD20+, B cell Lymphoma, Gray Zone Lymphoma,
or Hodgkin's Lymphoma

[figure not shown]
Standard Therapy

[figure not shown]
High-dose Consolidation Therapy

Registration for This Protocol

[figure not shown]
Evaluation of Eligibility for Protocol Participation

6 to 10 weeks after Initiation of High-dose Consolidation
Therapy for Maintenance Rituximab and Everolimus for 1 year

Treatment Evaluations with Radiographs, standard laboratories
and examination for 3 years/correlative peripheral blood
studies for 3 years

Follow-Up for 2 additional years to assess survival/disease status only

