The Sidney Kimmel Comprehensive Cancer center has pioneered the concept of high-dose cyclophosphamide without stem cell rescue for over a decade. This high-dose consolidative treatment was developed for two main reasons.

It does not require stem cell rescue: it eliminates the potential of cancer re-introduction at time of stem cell rescue. Moreover, as this high-dose therapy does not require stem cell rescue all the components of autologous stem cell transplant: collection, preservation and re-infusion are eliminated making this therapy a more widely available treatment modality.

Tolerability: not only are the majority of the patients treated with this modality served in the outpatient setting, many have had a performance status or advanced age not otherwise well suited for an autologous stem cell transplant.

We put forward that the cytoreduction achieved by high-dose consolidative cyclophosphamide represents the ideal foundation for the integration of novel molecularly targeted compounds for these lymphomas.

81 adults received, as outpatients, rituximab [375mg/m² days 1, 4, 8, 11, 45, 52] and cyclophosphamide [50mg/kg days 15-18 with concurrent mesna] and pegfilgrastim (day +20). Forty-two participants had low grade B cell lymphoma [grade I/II follicular (69%), transformed lymphoma (17%), other (15%)]: 45% were treated without measurable disease. Thirty-nine had mantle cell lymphoma: 82% were treated without measurable disease. All achieved hematopoietic recovery; 46% required brief hospitalizations. The EFS for low grade B cell patients at 3 and 5 years was 49% and 40% with an overall survival (OS) at 3 and 5 years of 86% and 72%. The 3 and 5 year EFS for MCL patients was 57% and 39% with a 3 and 5 year OS 92% and 62%.

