Hodgkin's data: Rituximab, high dose cy, and GM-CSF based immunotherapy for relapsed Hodgkin's lymphoma: This phase I/II, single-institution trial for relapsed classical Hodgkin lymphoma has just completed accrual of its planned 30 patients. Clinical outcomes of this platform, which was developed as a potentially less toxic alternative to autologous BMT, are encouraging. In the first 25 patients, whose median time between first-line therapy completion and relapse was 12 months, actuarial event-free survival is 79% at 1 year and 63% at 2 and 3 years following high-dose cyclophosphamide; overall survival is 100% at 2 years and 92% at 3 years. These early results are comparable to what is seen with autologous BMT. The toxicity profile has been manageable, and there has been no treatment-related mortality. Median time to neutrophil recovery after high dose cyclophosphamide was 17 days, and 21 days for platelet recovery with 5 patients not

requiring platelet transfusion. The trial was presented in a poster session at the 52nd American Society of Hematology annual meeting (Kasamon Y et al, *Blood* 2010, abstract 3954).

2.0 Primary Study Objective:

To determine the safety of maintenance rituximab and prolonged mTOR inhibition with everolimus in CD20+, B cell lymphomas, Gray Zone Lymphoma, and Hodgkin's Lymphoma after high-dose consolidative therapy.

- Safety will be determined by the extent of avoidance of \geq grade III common toxicities (CTCAE version 4.0)

2.1 Secondary Objectives:

- 1) The secondary endpoint of this study is to evaluate event free survival (EFS) at three years based on histology.
 - EFS will be histology grade specific: Mantle cell lymphoma group, low-grade lymphoma group, high-grade lymphoma group
- 2) To determine whether maintenance rituximab with everolimus treatment reduces the frequency of circulating cancer cells.
- 3) To determine if relapsed disease is sensitive, in-vivo, to mTor kinase inhibition.

3 Investigational plan

3.1 Overall study design: After high dose consolidative therapy, patient will receive one year of adjuvant rituximab and everolimus. Treatment evaluation with radiographs, standard laboratories and examination will follow for the next three years. Survival/disease status will also be assessed for an additional two years, for up to 5 years total of follow-up.

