3.2 Study population

Lymphoma histologies:

Mantle cell lymphoma

- Biopsy-proven diagnosis of Mantle Cell Lymphoma per the World Health Organization classification criteria
- The diagnosis is to be based on histologic and immunophenotypic criteria and include either immunohistochemical analysis for cyclin D1, cytogenetic analysis be either conventional karyotyping or fluorescence in situ hybridization (FISH) for 9(11;14)(q13;32), or both.
- Patient had met institutional standards for having high-dose consolidative therapy

Non-Mantle cell low grade B cell lymphomas (including SLL/CLL)

- Biopsy-proven diagnosis of lymphoma per the World Health Organization classification criteria
- Patient had met institutional standards for having high-dose consolidative therapy and relapsed disease despite the use of at least one chemotherapeutic agent (single agent Rituximab does not qualify for these histologies)
- Exception for mantle cell lymphoma and high risk SLL/CLL [defined as: del(17p), del (11q), or del(13q) concurrent with an unmutated IGVH status] who received high-dose consolidative therapy in first response are eligible for this protocol.

Transformed lymphoma/DLBCL/High risk DLBCL in first response/PMBCL

- Biopsy-proven diagnosis of lymphoma per the World Health Organization classification criteria
- Patient had met institutional standards for having high-dose consolidative therapy.

Gray Zone Lymphoma in first CR

- Biopsy-proven diagnosis of lymphoma per the World Health Organization classification criteria
- Patient had met institutional standards for having high-dose consolidative therapy.

Hodgkin's Disease

- Biopsy-proven diagnosis of lymphoma per the World Health Organization classification criteria
- Patient had met institutional standards for having high-dose consolidative therapy.

3.2.1 Patient population Patients must have had chemotherapy responsive disease (Partial response or better) before high-dose consolidative therapy. The accrual rate for this study is expected to be 20 patients per year. Assuming a three year recruitment period with a minimum follow-up of one year, 60 patients will give us 85% power to detect a 20% increase in EFS: 49% to 69%. Inclusion and exclusion criteria

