3.3 Treatment

Pre-treatment evaluation (to be completed ≤ 30 days before treatment initiation)

History and Physical Examination

History should try to document the pre high dose consolidative therapy MIPI score (age at diagnosis, ECOG performance status, LDH and WBC) and FLIPI score (age of diagnosis, LDH, ECOG performance status, number of extranodal sites, Ann Arbor stage) for Mantle and follicular lymphoma patients, respectively.

A detailed assessment of Hepatitis B/C medical history and risk factors must be done for all patients at screening, with testing performed prior to the first dose of everolimus. Please see Addendum 8 for action to be taken for patients with a positive baseline hepatitis B result.

CBC with platelet and reticulocyte count

Complete metabolic panel, immunoglobulin panel (IGG, IGA, IGM), fasting triglycerides, glucose and total cholesterol (cholesterol and triglycerides can be measured on either the screening visit or the day 1 visit)

PET/CT scans. If PET/CT is not possible a CT of the chest/abdomen/pelvis is required.

Bone marrow aspirate and biopsy: if bone marrow was previously involved

HCG urine pregnancy test for women of child bearing potential

Treatment initiation: treatment is to begin between six (6) weeks and ten (10) weeks after high dose consolidative therapy

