The non-parametric Kaplan-Meier estimate will be used to estimate the EFS function at one year. After 20 patients have been enrolled, the design will include interim analyses for futility that could halt the trial if it seems likely that the drug combination does not have sufficient clinical activity.

The sample size of 60 and the study design operating characteristics assume a three-year recruitment period with an additional follow-up of one year. Based on a study of high dose cyclophosphamide and rituximab without stem cell transplantation at our institution [2], the one and three-year EFS for low grade B cell lymphomas was 67 and 49% respectively. The simulation below demonstrates how the operating characteristics of the design varies when the uncertainty of the one-year EFS is characterized with the prior: beta(3,2). This implies that our prior guess at one-year EFS for these patients is 60%, and there is 90% probability that the EFS at 12 months is between 25% and 90%.

We have designed this study to stop early only if it appears that this treatment is associated with a lower one-year EFS than 50%. Specifically, the stopping rule will hold enrollment if the posterior probability of one-year EFS being less than 50% is 70% or higher. Simulations were carried out with exponential survival and staggered patient entry. We assumed, on average, 2 patients would enter the study per month. Interim analyses began once 20 patients entered the study and occurred after groups of 10 patients thereafter, up to a maximum of 60 patients. The interim analysis estimates of one-year EFS are based on analyses with an underlying Dirichlet process prior. We approximated the posterior distribution, which is actually a mixture of Beta distributions, the mixture depending on the amount of censoring, with a single Beta distribution. The parameters of this posterior Beta distribution are based on the number of failures and the effective sample size at 12 months, combined with the parameters of the prior. The following tables summarize the operating characteristics under various scenarios for the underlying exponential EFS, based on 1000 simulations. The 95% posterior intervals are the quantiles of

the simulated one-year EFS corresponding to probabilities of .025 and .957. The interpretation is that the posterior probability that the estimate of one-year PFS lies in this interval is 95%.

Prior is beta(3,2) : Mean is 0.60

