1-yr EFS	Prob Stop for Futility	Avg N	Est 1- yr PFS	Lo 95% Post Int'l	Hi 95% Post Int'l	Prob H0 Rejected
0.45	0.60	40.3	0.42	0.25	0.58	0.03
0.5	0.37	47.7	0.47	0.25	0.62	0.12
0.55	0.17	54.1	0.53	0.35	0.67	0.28
0.60	0.07	57.5	0.59	0.40	0.72	0.57
0.65	0.02	59.1	0.64	0.50	0.77	0.83
0.70	0.01	59.8	0.70	0.58	0.82	0.96

Analysis of primary objective:

The proportion of patients positive for the toxicity evaluation as defined for this study: patients for which the minimum 2.5 mg everolimus every other day was not tolerable or any unexpected hospitalizations during protocol participation will be reported with an exact binomial calculation and 95% confidence interval. The proportion of patients requiring dose adjustments down as well as the proportion requiring dose adjustments up will be reported separately with confidence intervals. All other grade 1 and 2 toxicities will be reported by type and grade, overall and within intervals throughout the study (0, 60], (60, 90], (90,120], (120, 180], (180, 365] and (365, 1460].

Analysis of secondary objectives:

Standard life table methods will be used to analyze EFS. We will report the one and three-year EFS with 95% confidence intervals. The three-year EFS will be compared to the null EFS of 49% with a Z-score and a one-sided alpha level of 0.05.

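### The 49% null appears to be counted from the consolidation regimen, while trial EFS starts at a later registration, so the three-year test probably uses too low a null

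*Combined protocol and SAP*

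**What the plan says.** The test is in section 6.0, under the analysis of secondary objectives: "The three-year EFS will be compared to the null EFS of 49% with a Z-score and a one-sided alpha level of 0.05". Section 3.2.1 rests the sample size on the same figure: "60 patients will give us 85% power to detect a 20% increase in EFS: 49% to 69" (per cent), under the condition "Assuming a three year recruitment period with a minimum follow-up of one year".

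The figure comes from the institution's study of rituximab plus high-dose cyclophosphamide. Section 1.2 reports: "The EFS for low grade B cell patients at 3 and 5 years was 49% and 40" (per cent). Section 6.0 adds 67% at one year. That study describes 81 adults who received the regimen, 42 of them low-grade, and mentions no landmark or later selection point. It gives no time origin for EFS. The Hodgkin's series from the same institution, also in section 1.2, does give one: "actuarial event-free survival is 79% at 1 year and 63% at 2 and 3 years following high-dose cyclophosphamide".

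In this trial, sections 3.4.3 and 6.0 start EFS at registration. In the schema, "Registration for This Protocol" comes after high-dose consolidation and before the eligibility evaluation. Section 3.3 says "treatment is to begin between six (6) weeks and ten (10) weeks after high dose consolidative therapy" and allows screening up to 30 days before treatment. No landmark or conditional version of the 49% appears anywhere.

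**The concern.** A patient who dies between consolidation and registration can never enter this trial, and one who progresses in that interval has less chance of entering. If the historical clock starts at the regimen, the same patient is a failure in the 49%. The trial's three-year EFS is then conditional on reaching registration and the null is not.

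There is no control arm, so the validity of the test rests on the null. If the comparable no-benefit value is above 49%, a regimen that adds nothing rejects more often than 5% of the time, and the error favours the drug. Part of the planned 20-point gain would also come from the change of clock. This is separate from the histology mix: it would remain in a trial of low-grade patients only.

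**Working it through.** **Inputs.** N = 60, one-sided 0.05, 49% against 69%, three-year accrual with one-year minimum follow-up (sections 3.2.1 and 6.0). Historical low-grade EFS of 67%, 49% and 40% at 1, 3 and 5 years (sections 1.2 and 6.0). *Assumption:* registration falls L = 2 to 10 weeks after the historical time zero. The lower end is 6 weeks less the 30-day screening window (42 − 30 = 12 days); the upper end is the latest treatment start.

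**Step 1: the plan's power.** For a Z-test on the Kaplan-Meier estimate at three years, with exponential EFS, uniform accrual over three years and analysis at year 4:

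SE² = S(3)² × (1/60) × ∫₀³ λ / [S(t)G(t)] dt, where G(t) = 1 up to one year and (4 − t)/3 from one to three years.

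This gives SE = 0.0727 at 69% and 0.0799 at 49%. Power = Φ(0.20/0.0727 − 1.645) = Φ(1.105) = 86.5%, close to the stated 85%.

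**Step 2: the hazard in the historical figures.**
- Year 1: −ln(0.67) = 0.400 per year
- Years 1–3: ln(0.67/0.49)/2 = 0.156 per year
- Years 3–5: ln(0.49/0.40)/2 = 0.101 per year

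The hazard falls. A constant hazard through 49% at three years would give 0.49^(1/3) = 78.8% at one year and 0.49^(5/3) = 30.5% at five, against the stated 67% and 40%.

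**Step 3: the comparable null.** If everyone in the trial is event-free at L, the no-benefit three-year EFS is S(3+L)/S(L). With a flat hazard within each interval, S(L) = exp(−0.400L) and S(3+L) = 0.49 × exp(−0.101L), L in years.

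**Step 4: error and power.** With c the comparable null, true error = Φ((c − 0.49)/SE(c) − 1.645), where SE(c) is about 0.080 throughout. Power against 69% = Φ((0.69 − c)/0.0727 − 1.645).

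| L (weeks) | S(L) | S(3+L) | c | True one-sided error | Power for 69% against c |
|---|---|---|---|---|---|
| 2 | 0.985 | 0.488 | 49.6% | 5.8% | 84.8% |
| 6 | 0.955 | 0.484 | 50.7% | 7.6% | 80.8% |
| 10 | 0.926 | 0.481 | 51.9% | 10.0% | 76.0% |

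The historical share failing before L is 1.5% at 2 weeks and 7.4% at 10 weeks.

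**Step 5: sensitivity to the shape within year 1.**
- *Constant hazard:* S(3+L)/S(L) = 49% at every L, and the error stays at 5%.
- *Front-loaded failures:* a Weibull curve through 67% and 49% has shape 0.525 and predicts 39.3% at five years (stated: 40%). It gives c = 52.4%, 54.9% and 56.6% at 2, 6 and 10 weeks, errors of 11.2%, 18.5% and 24.9%, and power of 73.7%, 61.4% and 52.3%.

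**The case against.** The strongest objection is that the historical time zero is an inference. Neither section 1.2 nor section 6.0 says where the low-grade clock starts. The historical regimen itself runs from day 1 to day 52, and the explicit timing belongs to a different study in a different disease. This stands, and the point is conditional on the answer. But that cohort had no maintenance registration to count from, and the test cannot be interpreted until the plan states the origin.

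Second, no eligibility criterion excludes patients who progress between consolidation and registration. The response requirement applies before consolidation; blood counts, performance status and the four-week gap since other anticancer therapy are only indirect filters. This also stands. A reader might infer that the bias grows further if progressors found at baseline are excluded. It does not: S(3+L)/S(L) already assumes that all early failures are absent, so incomplete exclusion makes the shift smaller.

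Third, a reader might infer that the entry counts select patients who recovered from consolidation. Section 1.2 says every historical patient recovered hematopoiesis, so failure to recover removed nobody from the null cohort. The entry thresholds may be stricter, but the documents do not link them to EFS.

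Fourth, the plan models survival as exponential ("Simulations were carried out with exponential survival and staggered patient entry"), and under a constant hazard the shift is zero. Step 2 shows that the historical figures do not fit that model.

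Fifth, the effect is modest. Of 42 low-grade patients, 1.5 to 7.4% is about 0.6 to 3.1 people, and the binomial SE of the 49% is √(0.49 × 0.51/42) = 7.7 points. Applying a low-grade null to mantle cell patients (57% at three years) or Hodgkin's patients (63%) leaves larger gaps. Both are true, but neither removes a bias of known direction under a falling hazard.

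**Conclusion.** The point holds conditionally. If the 49% is timed from the consolidation regimen, it is not comparable with EFS from registration, and the mismatch favours the drug. With a flat year-1 hazard, registration 2 to 10 weeks after time zero, and all earlier failures absent from the trial, the comparable null is about 49.6 to 51.9%. The one-sided error is then about 6 to 10%, and power against 69% falls from about 86% to 76–85%. Front-loaded failures would enlarge this, as step 5 shows, but the documents give no event times within the first year.

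A reader might infer an error near 12%. That follows from SE = √(0.49 × 0.51/60) = 0.0645, which requires three full years of follow-up on all 60 patients; the stated one-year minimum does not provide it. Nor does the point reach the futility rule, which uses a 50% threshold and a beta(3,2) prior; the 67% enters no decision rule.

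The endpoint is secondary in a safety study. The correction is worth making because this is the trial's only formal efficacy test.

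**What to change.** State the time zero of the historical 49% in section 6.0. If it precedes registration, re-estimate three-year EFS in the institution's low-grade cohort among patients event-free at a landmark matching registration, for example 6 to 10 weeks after consolidation. Count the three years from that landmark, use the result in place of 49% in the test, and restate the power in section 3.2.1.

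Timing trial EFS from consolidation with delayed entry at registration is not a substitute. With nobody at risk before the earliest registration, it estimates S(3)/S(entry). At 6 weeks that is 0.49/0.955 = 51.3%, against 50.7% under the present definition, so the gap from 49% widens.

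The cost is a small re-analysis of the institution's own study data, revised wording, and somewhat lower stated power. No trial procedure changes.

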Co-administration with strong inhibitors of CYP3A4 (e.g., ketoconazole, itraconazole, ritonavir) or P-glycoprotein (PgP) should be avoided.

Co-administration with moderate CYP3A4 inhibitors (e.g., erythromycin, fluconazole) or PgP inhibitors should be used with caution. If patient requires co-administration of moderate CYP3A4 inhibitors or PgP inhibitors, reduce the dose of everolimus to half the currently used dose. Additional dose reductions to every other day may be required to manage toxicities. If the inhibitor is discontinued the everolimus dose should be returned to the dose used prior to initiation of the moderate CYP3A4/PgP inhibitor after a washout period of 2 to 3 days.

Seville orange, star fruit, grapefruit and their juices affect P450 and PgP activity. Concomitant use should be avoided.

Addendum 2: Inducers of CYP3A4 and/or PgP

If patients require co-administration of a strong CYP3A4 inducer, consider doubling the daily dose of Afinitor (based on pharmacokinetic data), using increments of 5 mg or less. This dose of Afinitor is predicted to adjust the AUC to the range observed without inducers. However, there are no clinical data with this dose adjustment in patients receiving strong CYP3A4 inducers. If the strong inducer is discontinued, consider a washout period of at least 3 to 5 days (reasonable time for significant enzyme de-induction), before the Afinitor dose is returned to the dose used prior to initiation of the strong CYP3A4 inducer.

This dose adjustment of everolimus is intended to achieve similar AUC to the range observed without inducers. However, there are no clinical data with this dose adjustment in patients receiving strong CYP3A4 inducers. If the strong inducer is discontinued the everolimus dose should be returned to the dose used prior to initiation of the strong CYP3A4/PgP inducer.

Addendum 3: Clinically relevant drug interactions: substrates, inducers, and inhibitors of isoenzyme CYP3A

SUBSTRATES	
Antibiotics: Clarithromycin, erythromycin, telithromycin	Calcium channel blockers: Amlodipine, diltiazem, felodipine, lercanidipine, nifedipine, nisoldipine, nitrendipine, verapamil
Anti-arrhythmics: Quinidine	HMG CoA reductase inhibitors: Cerivastatin, lovastatin, simvastatin
Benzodiazepines: Alprazolam, diazepam, midazolam, triazolam	Steroid 6beta-OH: estradiol, hydrocortisone, progesterone, testosterone
Immune modulators: Cyclosporine, tacrolimus (FK506)	Miscellaneous: Alfentanil, aprepitant, aripiprazole, buspirone, cafergot, caffeine, cilostazol, cocaine, codeine-N-demethylation, dapsone, dexamethasone, dextromethorphan, docetaxel domperidone, eplerenone, fentanyl, finasteride, Gleevec/imatinib, haloperidol, irinotecan, LAAM, lidocaine, methadone, nateglinide, ondansetron, pimozide, propranolol, quetiapine, quinine, risperidone, salmeterol, sildenafil, sirolimus, sorafenib, sunitinib, tamoxifen, taxol, terfenadine, torisel, trazodone, vincristine, zaleplon, ziprasidone, zolpidem
HIV Antivirals: Indinavir, nelfinavir, ritonavir, saquinavir	
Prokinetic: Cisapride	
Antihistamines: Astemizole, chlorpheniramine, terfenadine	
INDUCERS	
Strong inducers: avasimibe, carbamazepine, mitotane, phenobarbital, phenytoin, rifabutin, rifampin (rifampicin), St. John's wort (hypericum perforatum)	

Moderate inducers:

bosentan, efavirenz, etravirine, genistein, modafinil, nafcillin, ritonavir, [talviraline], thioridazine, tipranavir

Weak inducers:

amprenavir, aprepitant, armodafinil (R-modafinil), bexarotene, clobazam, danshen, dexamethasone, Echinacea, garlic (allium sativum), gingko (ginkgo biloba), glycyrrhizin, methylprednisolone, nevirapine, oxcarbazepine, pioglitazone, prednisone, [pleconaril], primidone, raltegravir, rufinamide, sorafenib, telaprevir, terbinafine, topiramate, [troglitazone] , vinblastine

INHIBITORS**Clinically relevant drug interactions mediated by PgP**

PgP Substrates	PgP Inhibitors and PgP/CYP3A Dual Inhibitors	PgP Inducers
digoxin, fexofenadine, indinavir, vincristine, colchicine, topotecan, paclitaxel, talinolol, everolimus	amiodarone, azithromycin, captopril, carvedilol, clarithromycin, conivaptan, diltiazem, dronedarone, elacridar, erythromycin, felodipine, (GF120918), fexofenadine, fluvoxamine, ginko (ginkgo biloba), indinavir, itraconazole, lopinavir, (LY335979), mibepradil, milk thistle (silybum marianum), nelfinavir,	rifampin, St John's wort

Confidential

Clinical study protocol number: J1228

Page 49

Version Date: May 7, 2018

IRB study Number: NA_00067315

PgP Substrates	PgP Inhibitors and PgP/CYP3A Dual Inhibitors	PgP Inducers
	nifedipine, nitrendipine, (PSC833), paroxetine, quercetin, quinidine, ranolazine, rifampin, ritonavir, saquinavir, Schisandra chinesis, St John's wort (hypericum perforatum), talinolol, Telaprevir, telmisartan, ticagrelor, tipranavir, tolvaptan valspar, verapamil	

Reference: Internal Clinical Pharmacology Drug-drug interaction (DDI) memo, updated Oct. 2, 2011, 29-Oct-2012 which summarizes DDI data from three sources including the FDA's "Guidance for Industry, Drug Interaction Studies", the University of Washington's Drug Interaction Database, and Indiana University School of Medicine's Drug Interaction Table.

Addendum 4: Dose Modifications for abnormal serum drug concentrations without grade III/IV toxicities, grade \geq III toxicities (CTCAE version 4.0) except for stomatitis and lipid/hyperglycemia toxicities

- Patient will have regularly scheduled everolimus levels drawn throughout the study
- Everolimus is available in 2.5mg, 5mg and 10mg strengths
- The reference range for patients experiencing a <II common toxicity (CTCAE version 4.0) is 3-15ng/mL
- Anytime a dose is adjusted, repeat everolimus serum trough levels will be re-drawn 14 days (\pm 3 days) later. As clinically possible, all patients' other labs will be reset to match this new everolimus serum trough level schedule.
- Once everolimus is held due to high serum trough levels, everolimus should be held for 7 days before restarting at a lower dose level.
- During a treatment hold, everolimus levels will not be drawn once the serum trough level is less than 1.0.
- There is no limit on how long a patient can be on everolimus treatment hold. Labs will be monitored every two weeks while the patient is on hold.
- For patients >15 ng/mL or <3.0 ng/mL and not experiencing >II grade common toxicity, their dose will be adjusted by $+/-.2.5$ mg/day; lowest dose allowed is 2.5mg every 4 days. The study nurse will provide a calendar to patients when the dose level is 2.5 mg taken every 3 or 4 days
- If a patient on a schedule of 2.5 mg (QOD) or lower misses a dose, that dose should be made up.
- Non-hematologic grade \geq III CTCAE toxicities: hold drug until CTCAE toxicity is (I) but can be continued at grade 2 if the baseline values were within the range of grade 2 and restart at a dose level -2.5mg/day. Lowest dose allowed is 2.5mg every 4 days
- Grade 4 or 4 clinical failure – discontinue RAD001
- Recurrence of grade 4 toxicity after dose reduction – discontinue RAD001
- Hematologic grade \geq III CTCAE toxicity
 - Anemia
 - Hgb <8.0 g/dL: transfuse RBC; hold drug for 7 days or until Hgb >10 mg/dL (untransfused): whichever is longer. Restart at a dose - 2.5mg/day. Lowest dose allowed is 2.5mg every 4 days
 - Thrombocytopenia
 - Platelets $< 50,000$: hold drug until platelet count is $>75,000$ and restart at a dose level -2.5mg/day. Lowest dose allowed is 2.5mg every 4 days

- Platelets <10,000: transfuse PLT: when platelet count is >75,000 (transfusion independent: at least 7 days). Restart at a dose level -2.5mg/day; lowest dose allowed is 2.5mg every 4 days
- Neutropenia:
 - ANC <1,000/mm³ hold drug (and rituximab) until ANC >1,500 and restart at a dose level -2.5mg/day. Lowest dose allowed is 2.5mg every 4 days
 - No adjustments will be made for lymphopenia
- Lowest dose allowed on protocol is 2.5mg every 4 days. If serum concentrations on this dosing schedule are >15ng/mL or if on this dosing schedule greater than grade II toxicities are experienced the patient will be taken off study. However, patients will be followed until toxicities return to grade 1 or baseline as appropriate.

Addendum 5: Management of stomatitis/oral mucositis/mouth ulcers

Management of stomatitis / oral mucositis / mouth ulcers

Adverse Drug Reaction	Severity	Afinitor Dose Adjustment and Management Recommendations
Stomatitis	Grade 1 (Minimal symptoms, normal diet)	No dose adjustment required. Manage with non-alcoholic or salt water (0.9%) mouth wash severaltimes a day.
	Grade 2 (Symptomatic but can eat and swallow modified diet)	Temporary dose interruption until recovery to grade ≤ 1 . Re-initiate Afinitor at the same dose. If stomatitis recurs at grade 2, interrupt dose until recovery to grade ≤ 1 . Re-initiate Afinitor at a lower dose. Manage with topical analgesic mouth treatments (e.g. benzocaine, butyl aminobenzoate, tetracaine hydrochloride, menthol or phenol) with or without topical corticosteroids (i.e. triamcinolone oral paste)*.
	Grade 3 (Symptomatic and unable to adequately eat or hydrate orally)	Temporary dose interruption until recovery to grade ≤ 1 . Re-initiate Afinitor at lower dose. Manage with topical analgesic mouth treatments (i.e. benzocaine, butyl aminobenzoate, tetracaine hydrochloride, menthol or phenol) with or without topical corticosteroids (i.e. triamcinolone oral paste)*
	Grade 4 (Symptoms associated with life-threatening consequences)	Discontinue Afinitor and treat with appropriate medical therapy.

* using agents containing alcohol, hydrogen peroxide, iodine, and thyme derivatives in management of stomatitis as they may worsen mouth ulcers.

Patients with a clinical history of stomatitis/mucositis/mouth ulcers and those with gastrointestinal morbidity associated with mouth/dental infections, irritation of esophageal mucosa e.g. gastroesophageal reflux disease (GERD) and pre-existing stomatitis/mucositis must be monitored even more closely. Patients should be

instructed to report the first onset of buccal mucosa irritation/reddening to their study physician immediately.

Stomatitis/oral mucositis/mouth ulcers due to Everolimus should be treated using local supportive care. Please note that investigators in earlier trials have described the oral toxicities associated with Everolimus as mouth ulcers, rather than mucositis or stomatitis. If your examination reveals mouth ulcers rather than a more general inflammation of the mouth, please classify the adverse event as such. The suggested paradigm for treatment of stomatitis/oral mucositis/mouth ulcers is as follows:

1. For mild toxicity (Grade 1), use conservative measures such as non-alcoholic mouth wash or salt water (0.9%) mouth wash several times a day until resolution.
2. For more severe toxicity (Grade 2 in which case patients have pain but are able to maintain adequate oral alimentation, or Grade 3 in which case patients cannot maintain adequate oral alimentation), the suggested treatments are topical analgesic mouth treatments (i.e., local anesthetics such as benzocaine, butyl aminobenzoate, tetracaine hydrochloride, menthol, or phenol) with or without topical corticosteroids, such as triamcinolone oral paste 0.1% (Kenalog in Orabase®).
3. Agents containing hydrogen peroxide, iodine, and thyme derivatives may tend to worsen mouth ulcers. It is preferable to avoid these agents.
4. Antifungal agents must be avoided unless a fungal infection is diagnosed. In particular, systemic imidazole antifungal agents (ketoconazole, fluconazole, itraconazole, etc.) should be avoided in all patients due to their strong inhibition of everolimus metabolism, thereby leading to higher everolimus exposures. Therefore, topical antifungal agents are preferred if an infection is diagnosed. Similarly, antiviral agents such as acyclovir should be avoided unless a viral infection is diagnosed.

Addendum 6: Management of hyperlipidemia and hyperglycemia

Treatment of hyperlipidemia should take into account the pre-treatment status and dietary habits. Blood tests to monitor hyperlipidemia must be taken in the fasting state. Hyperlipidemia and hypertriglyceridemia should be treated according to local best clinical practice. Patients should be monitored clinically and through serum chemistry for the development of rhabdomyolysis and other adverse events as required in the product label/data sheets for HMG-CoA reductase inhibitors.

Management of hyperlipidemia and hyperglycemia

Adverse Drug Reaction	Severity	Afinitor Dose Adjustment and Management Recommendations
Metabolic events (e.g. hyperglycemia, dyslipidemia)	Grade 1	No dose adjustment required. Initiate appropriate medical therapy and monitor.
	Grade 2	No dose adjustment required. Manage with appropriate medical therapy and monitor.
	Grade 3	Temporary dose interruption. Re-initiate Afinitor at lower dose. Manage with appropriate medical therapy and monitor.
	Grade 4	Discontinue Afinitor and treat with appropriate medical therapy.

Dyslipidemia (including hypercholesterolemia and hypertriglyceridemia) has been reported in patients taking everolimus. Monitoring of blood cholesterol and triglycerides prior to the start of everolimus therapy and periodically thereafter as well as management with appropriate medical therapy is recommended.

Hyperglycemia has been reported in patients taking everolimus. Monitoring of fasting serum glucose is recommended prior to the start of everolimus therapy and periodically thereafter. More frequent monitoring is recommended when everolimus is co-administered with other drugs that may induce hyperglycemia. Optimal glycemic control should be achieved before starting trial therapy.

Addendum 7: Management of non-infectious pneumonitis

Non-infectious pneumonitis is a class effect of rapamycin derivatives. Cases of non-infectious pneumonitis (including interstitial lung disease) have also been described in patients taking everolimus. Some of these have been severe and on rare occasions, a fatal outcome was observed.

A diagnosis of non-infectious pneumonitis should be considered in patients presenting with non-specific respiratory signs and symptoms such as hypoxia, pleural effusion, cough or dyspnoea, and in whom infectious, neoplastic and other non-medicinal causes have been excluded by means of appropriate investigations. Opportunistic infections such as PJP should be ruled out in the differential diagnosis of non-infectious pneumonitis. Patients should be advised to report promptly any new or worsening respiratory symptoms.

Patients who develop radiological changes suggestive of non-infectious pneumonitis and have few or no symptoms may continue Afinitor therapy without dose alteration.

If symptoms are moderate (grade 2), consideration should be given to interruption of therapy until symptoms improve. The use of corticosteroids may be indicated. Afinitor may be reintroduced at a daily dose approximately 50% lower than the dose previously administered.

For cases of grade 3 non-infectious pneumonitis, interrupt Afinitor until resolution to less than or equal to grade 1. Afinitor may be re-initiated at a daily dose approximately 50% lower than the dose previously administered depending on the individual clinical circumstances. If toxicity recurs at grade 3, consider discontinuation of Afinitor. For cases of grade 4 non-infectious pneumonitis, Afinitor therapy should be discontinued. Corticosteroids may be indicated until clinical symptoms resolve.

For patients who require use of corticosteroids for treatment of non-infectious pneumonitis, prophylaxis for pneumocystis jirovecii pneumonia (PJP) may be considered. The two compounds studied most extensively for prophylaxis against PJP have been trimethoprim-sulfamethoxazole, given orally, and pentamidine, given as an aerosol.

If non-infectious pneumonitis develops, the guidelines in the table below should be followed. Consultation with a pulmonologist is recommended for any case of pneumonitis that develops during the study.

Management of non-infectious pneumonitis

Worst grade pneumonitis	Suggested investigations	Management of pneumonitis	Everolimus dose adjustment
Grade 1 (Asymptomatic, radiographic findings only)	CT scans with lung windows.	No specific therapy is required	No dose adjustment required. Initiate appropriate monitoring.
